6.4.3.2 Secondary Objectives Analyses, if applicable

Secondary analyses will explore three research questions: (1) Does smartphone program (*iCanCope-NF*) compared with control condition lead to differences in pain and pain-related activity limitations, sleep functioning, emotional functioning (depression, anxiety), pain catastrophizing, self-efficacy, knowledge, psychological flexibility immediately post-treatment (T2)? This will be evaluated by incorporating an estimating equation approach to understand the differences in scores and using a sequential multilevel logistic regression models to estimate the independent and combined effects of proposed time-varying (contextual) variables on the probability of pain levels. We will also test interaction effects between stable/trait-level participant characteristics and contextual variables. (2) Does the *iCanCope-NF + CM* increase the usage of the *iCanCope-NF* program as compared to *iCanCope-NF* without CM, and do their corresponding levels of pain and pain-related activity decrease? This will be evaluated between the two intervention groups and using the difference in nominal data sets, and simple qualitative analyses. (3) Do individuals with NF1 utilize the MBAA more readily because they are on the mobile application? To assess the moderation effect, we will include an interaction term for each separate moderator variable and key predictor of interest (two-way interaction between moderator and group for cross-sectional analysis and three-way interaction between moderator, group and time for longitudinal analysis) in the regression models and test its significance using Wald t-test.

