5.2 Outcome Variables

5.2.1 Primary Outcome Variables

Primary Outcome Measure:

1. Engagement Activity

Total minutes logged on the mobile application will be evaluated between the two groups using the mobile application.

[Time Frame: through the completion of the study, on average 4 months.]

2. Pain Severity

A comparison within groups change of pain severity measured by the Brief Pain Inventory-Short Form. Respondents rate items on a 0-10 scale to indicate the pain severity and interference, and the total score is the mean of each subfactor. The higher the score indicates more severity and interference of pain.

[Time Frame: through the completion of the study, on average 4 months.]

3. Pain Interference Index

A comparison within groups change of pain interference measured by the Pain Interference Index Scale. Respondents rate items on a 0-6 scale to indicate how much pain has interfered with various activities, and the total score is the mean of the six items. Where 6 indicates high interference.

[Time Frame: through the completion of the study, on average 4 months.]

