5.3.2 Eligibility Criteria/Vulnerable Populations

Patients will be included in the study if they meet the following inclusion criteria:

- 1) adults older than age of 18
- 2) diagnosis a diagnosis of NF1;
- 3) permanently reside in the United States and
- 4) have pain interference aggregate scores of three or more in the last two weeks using the Brief Pain Inventory-Short Form (BPI-SF) scale.

Patients will be excluded if they: 1) have an undiagnosed case of NF1; 2) have documented major co-occurring psychiatric disease; 3) have moderate to severe cognitive deficits; or 4) have depression assessed using the Patient Health Questionnaire (PHQ-9) or anxiety assessed using the Generalized Anxiety Disorder scale (GAD-7) greater than or equal to the appropriate thresholds (10=mild major depression; 5=mild severe anxiety).

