6.4 Statistical Method

6.4.1 Statistical Design

Statistical procedures and models have been selected according to the research questions being investigated and the types of data available. We will use $\alpha < .05$ but will use appropriate corrections for multiple tests. Statistical analyses will be conducted by principal investigator using SPSS, SAS, or R with consultation from the coinvestigators. Using logistic regression for categorical and ANOVA for continuous measures, we will conduct preliminary analyses of the adequacy of the randomization procedure, the comparability of baseline measures across conditions, and the possible need for covariates in the analyses of treatment outcome data.

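### The model for contextual predictors of pain is logistic on undefined pain levels, although pain is scored as a numeric mean; modelling the score would avoid the loss

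*Combined protocol and SAP*

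**What the plan says.** Section 6.4.3.2, repeated word for word in 6.4.3, gives two methods under secondary question 1. The first is "incorporating an estimating equation approach to understand the differences in scores". The second is "sequential multilevel logistic regression models to estimate the independent and combined effects of proposed time-varying (contextual) variables on the probability of pain levels". The next sentence adds: "We will also test interaction effects between stable/trait-level participant characteristics and contextual variables". It names no model of its own.

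Section 5.2.1 defines the two pain outcomes as numbers. For the BPI-SF: "Respondents rate items on a 0-10 scale to indicate the pain severity and interference, and the total score is the mean of each subfactor". For the Pain Interference Index: "the total score is the mean of the six items. Where 6 indicates high interference". Six items scored 0 to 6 give 6 × 6 + 1 = 37 possible values of the mean.

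The only cut-off for a pain score is an entry criterion in section 5.3.2: participants must "have pain interference aggregate scores of three or more in the last two weeks using the Brief Pain Inventory-Short Form (BPI-SF) scale". It is not offered as an outcome threshold.

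**The concern.** A logistic model needs a categorical outcome, and the pain measures in section 5.2.1 are not categorical. Some grouping has to come between score and model, and the plan describes none. Three things follow.

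- **Information.** Grouping a numeric score discards the variation within each group. With a cut at 4, for example, a fall from 7 to 5 counts as no change.
- **Freedom of choice.** Odds ratios depend on where the categories lie, and nothing stops them being settled after the data are seen. Section 6.4.1 promises "but will use appropriate corrections for multiple tests", but names no method and does not address a choice among cut points.
- **No stated reason.** For its preliminary analyses (6.4.1) the plan pairs logistic regression with categorical measures and ANOVA with continuous ones. It also uses linear mixed models for engagement (6.4.3.1) and for coping-skills efficacy (6.4.3.3). It does not explain why pain is treated differently here.

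Borrowing the entry criterion would not solve this: every eligible participant would be in the upper category on that scale at entry.

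**Working it through.** The protocol states no figure for this loss, so there is none to reproduce.

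**Inputs.** From the protocol: the model type (6.4.3, 6.4.3.2), numeric pain scores (5.2.1), and no categories, cut point or link. Assumed: a roughly normal score, small predictor effects (so that large-sample relative efficiency applies), and illustrative splits.

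**Step 1: one binary cut.** Let c be the cut in SD units, φ the standard normal density and p the share above the cut. Efficiency relative to the uncut score is φ(c)² / [p(1 − p)].

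| Split | c | φ(c) | Efficiency | Lost |
|---|---|---|---|---|
| 50/50 | 0 | 0.3989 | 0.1592 / 0.25 = 0.637 | 36% |
| 30/70 | 0.524 | 0.3477 | 0.1209 / 0.21 = 0.576 | 42% |
| 20/80 | 0.842 | 0.2800 | 0.0784 / 0.16 = 0.490 | 51% |
| 10/90 | 1.282 | 0.1755 | 0.0308 / 0.09 = 0.342 | 66% |

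The median is the best place for a single cut of a normal score, so 1 − 2/π = 36.3% is the minimum loss.

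**Step 2: ordered levels.** Take k equal-sized levels with p_j = 1/k, scores s_j = 0, 1, …, k − 1, and m_j the normal density at the lower edge of level j minus that at its upper edge. The efficiency of a proportional-odds model is (Σ s_j m_j)² / Σ p_j (s_j − s̄)².

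For k = 3 the cuts are at ±0.431, where φ = 0.3636, so m = (−0.3636, 0, 0.3636). The numerator is (2 × 0.3636)² = 0.529, the denominator is 2/3, and the efficiency is 0.793: 21% lost. The same formula gives:

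| Levels | Efficiency | Lost |
|---|---|---|
| 3 | 0.793 | 21% |
| 4 | 0.856 | 14% |
| 5 | 0.888 | 11% |
| 7 | 0.918 | 8% |
| 11 | 0.938 | 6% |

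**Step 3: shape of the score.** For a median cut the efficiency is 4 f² σ², with f the density at the median and σ the SD. A logistic-shaped score gives π²/12 = 0.822 (18% lost), a t distribution with 10 df 0.757 (24%), one with 5 df 0.961 (4%), and a uniform score 1/3 (67%). The loss is smaller with heavier tails and larger with flatter scores. The 36% minimum therefore holds only for a near-normal score.

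**Step 4: what the figures describe.** They are relative losses per observation for the effect of a predictor on pain. They are not power for this model. Power would also need the predictor effect, the number of repeated measures and the within-participant correlation, none of which is stated for it.

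**The case against.** Several points on the other side stand, and they limit the finding.

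- **The wording allows more than two categories.** A reader might infer that the score must be split at a single threshold and that a third or more of its information is therefore lost. The plan speaks of levels in the plural and never says binary. An ordinal or multinomial model fits, and the ordinal loss can be as low as about 6%.
- **The outcome may not be the questionnaires.** App users are encouraged to make daily diary entries and check-ins (6.1.1, 6.3.1), while questionnaires come only at intake, discharge and follow-up (6.2.1). Time-varying predictors fit diary data at least as well. The diary's pain scale is not described, so whether anything would be cut there cannot be known.
- **The treatment comparison has its own method.** A reader might infer that the between-arm comparison loses power, or that 36 per arm shrinks to a smaller effective number. The estimating-equation clause in the same sentence addresses differences in scores, so two-arm power calculations do not measure this problem.
- **The interactions are logistic only by position.** The trait-by-context sentence follows the logistic model but names none. The moderator terms of question 3 go "in the regression models and test its significance using Wald t-test", with the type of regression unstated.
- **The analysis is exploratory**, within the secondary questions of a pilot trial.

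One thing survives all of this: no model of a numeric pain score is named for the contextual effects, and on every reading the categories, link and pain measure are missing.

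**Conclusion.** The concern holds for the contextual-predictor model of secondary question 1. With a near-normal score, the information lost on predictor effects is at least 36% under one binary cut, and about 21% down to 6% under an ordinal model with 3 to 11 equal-sized levels. The documents do not show which applies. The loss would extend to the trait-by-context interactions if they are fitted in the same model, which the order of the sentences suggests but does not establish. The freedom to choose categories after seeing the data is present on either reading.

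These sizes rest on approximate normality, small effects and the assumed splits. Because the analysis is secondary and exploratory, this should be corrected but does not threaten the trial's main comparisons. It goes beyond asking for a threshold to be written down: where the score is numeric, modelling it avoids the loss.

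**What to change.** In sections 6.4.3 and 6.4.3.2:

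1. Name the pain measure for the contextual model: the BPI-SF severity and Pain Interference Index means or, if that is what is intended and it is numeric, the daily app pain rating. The choice determines who is analysed, because the control group has no app during the trial.
2. Replace the multilevel logistic models with multilevel linear (mixed) models of that numeric score, with a participant random intercept and the same sequential entry of contextual variables.
3. State that the trait-by-context interactions are tested in that same model.
4. If a pain-level category is wanted, fix its cut point before any data are seen and use it for description only.

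The cost is wording in two sections. If the measure named is already collected, no new data, participants or software are needed. The small downside is that effects are reported in scale points instead of odds ratios.

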3.2 Purpose of Study/Potential Impact

We expect individuals with NF1 utilizing the iCanCope program to have decreased pain severity and interference if they regularly engage in the program. In addition, due to the added contingency management, we expect to see differences between the intervention groups (*iCanCope-NF* and *iCanCope-NF +CM*). By adding contingencies to increased engagement the CM grouping should have more improvements in pain intensity and pain interference in addition to current iCanCope processes. If we demonstrate initial feasibility and preliminary impact, in collaboration with Drs. [name] and [name], a definitive RCT will be conducted. In future studies, evaluating the sustainability of impact on the outcomes over the course of 12 months is critical to sustaining the impact of the application as well as generalization of treatment. Thus, following the patients in a 1, 3 and 6-month follow-up post-treatment is necessary.

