6.1.4 Intervention Administration

Individuals assigned to the *iCanCope-NF*, *iCanCope-NF +CM* will have 8 weeks of 24-hour access to the program. Individuals assigned the Control will not have access to the *iCanCope-NF* application.

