Secondary analyses will explore three research questions: (1) Does smartphone program (*iCanCope-NF*) compared with control condition lead to differences in pain and pain-related activity limitations, sleep functioning, emotional functioning (depression, anxiety), pain catastrophizing, self-efficacy, knowledge, psychological flexibility immediately post-treatment (T2)? This will be evaluated by incorporating an estimating equation approach to understand the differences in scores and using a sequential multilevel logistic regression models to estimate the independent and combined effects of proposed time-varying (contextual) variables on the probability of pain levels. We will also test interaction effects between stable/trait-level participant characteristics and contextual variables. (2) Does the *iCanCope-*

NF + CM increase the usage of the *iCanCope-NF* program as compared to *iCanCope-NF* without CM, and do their corresponding levels of pain and pain-related activity decrease? This will be evaluated between the two intervention groups and using the difference in nominal data sets, and simple qualitative analyses. (3) Do individuals with NF1 utilize the MBAA more readily because they are on the mobile application? To assess the moderation effect, we will include an interaction term for each separate moderator variable and key predictor of interest (two-way interaction between moderator and group for cross-sectional analysis and three-way interaction between moderator, group and time for longitudinal analysis) in the regression models and test its significance using Wald t-test.

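### App plus contingency management v app alone: the method named for pain does not fit numeric scores or yield an estimate, Cox regression has no event, and the engagement methods are unranked

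*Combined protocol and SAP*

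**What the plan says.** **Pain, app+CM v app.** Section 3.2 of the combined protocol and SAP expects that "the CM grouping should have more improvements in pain intensity and pain interference", and 3.3.2 repeats this. Question (2) of the secondary analyses takes it up, asking about usage and pain in the two app arms. The method, in 6.4.3.2 and in the same words in 6.4.3, is: "This will be evaluated between the two intervention groups and using the difference in nominal data sets, and simple qualitative analyses". Question (1), which compares the app with control, has its own method: "This will be evaluated by incorporating an estimating equation approach to understand the differences in scores".

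**Pain scales.** Section 5.2.1 defines the Brief Pain Inventory-Short Form (BPI-SF) score as a mean of items rated 0 to 10, and the Pain Interference Index as a mean of six items rated 0 to 6. The contrast given there is "A comparison within groups change of pain severity measured by the Brief Pain Inventory-Short Form", with matching wording for interference.

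**Engagement.** Primary outcome 1 carries the label engagement activity and is defined so: "Total minutes logged on the mobile application will be evaluated between the two groups using the mobile application". Sections 6.4.3 and 6.4.3.1 list engagement activity, with logins and dropout, under a general linear model for counts. They then give levels of engagement to mixed models with an AR1 structure.

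**Cox regression and missing data.** The same paragraphs assign Cox regression to pre-post differences, with missing data as the reason. Section 6.4.4 lists no covariates. Section 6.4.5 says that different missing-data assumptions will be examined and that missing values will be coded as zero.

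**The concern.** The trial has a separate CM arm, and section 3.2 looks ahead to a definitive trial. That trial would need an estimate of what CM adds to pain relief, with its uncertainty. As written, the plan does not say how such an estimate would be produced. The word nominal is ambiguous, but no reading of it leads to a CM-minus-no-CM difference in a mean score.

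Cox regression models the time to an event. Applied to a change between questionnaires, it has nothing to model.

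For total minutes, the analyst could pick among methods after seeing the data, because none is marked as the one that counts.

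Replacing the pain method alone would not be enough. Zero is the best possible pain score, and section 6.3.6 says that people who leave early are not asked for the end-of-study survey. Section 2.1 presents CM as a way to raise retention. If it does, the zeros would fall more often in the arm without CM and would make that arm look better.

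**Working it through.** **1. Is there another method for the CM pain question?** Going through the analysis sections:

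- Estimating equations (6.4.3, 6.4.3.2): question (1), app v control.
- Interaction models (same sections): question (3), use of mindfulness-based approaches.
- AR1 mixed models (6.4.3, 6.4.3.1): engagement.
- Mixed model of module minutes (6.4.3.3): change in coping skills, not an arm comparison.
- Primary pain outcomes (5.2.1): change within groups.

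None supplies the CM pain contrast. The sentence for question (2) names the two arms. It gives no effect measure, model, time point, covariates or interval.

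**2. Cox regression.** Section 6.2.1 places the questionnaires at intake, discharge and follow-up. A change between fixed assessments is not an event time, and no event, time origin or censoring rule is stated. A missing score is not a censored time, so the method does not repair it.

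**3. Engagement.** Three methods touch it: the count model, the AR1 models and the nominal/qualitative method (for usage). Minutes are a duration, not a count. An AR1 structure needs repeated values per person, so it can serve daily or weekly minutes but not one total each.

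**4. Illustration: cost of treating the score as categories.** The plan gives no effect size, SD or power for this contrast, so there is no figure of its own to reproduce. Input from 6.4.2: 36 per arm. Assumed: two-sided 5%, normal scores, difference d = 0.5 SD, split at the midpoint.

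- Numeric: power = Φ(d√(n/2) − 1.96) = Φ(0.5 × 4.243 − 1.96) = Φ(0.161) = 56%.
- Split: proportions Φ(±0.25) = 0.599 and 0.401, difference 0.197. Power = Φ[(0.197 × √36 − 1.96 × √0.5) / √0.480] = Φ(−0.29) = 39%.
- For 80% power: 63 per arm numeric, 100 split, about 1.6 times as many.

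**5. Precision of the replacement analysis.** 95% half-width = t(68) × SD × √(1 − r²) × √(2/36), complete data. SD and baseline correlation r are assumed.

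| SD | r | Half-width (points) |
|---|---|---|
| 1.5 | 0.7 | 0.50 |
| 2.0 | 0.5 | 0.81 |
| 2.5 | 0.5 | 1.02 |

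**6. What zero-coding would do to it.** Assumed: post-treatment mean 4, SD 2 at both times, r = 0.6, no true difference, 20% missing without CM and 10% with CM.

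- Shift = gap in missingness × mean = 0.10 × 4 = 0.40 points against CM.
- Variance with zeros = (1 − m) × SD² + m(1 − m) × mean²: 3.20 + 2.56 = 5.76 at m = 0.20, and 3.60 + 1.44 = 5.04 at m = 0.10.
- Pooled slope on baseline = 0.85 × 0.6 = 0.51. Residual variances: 5.76 + 0.51² × 4 − 2 × 0.51 × 1.92 = 4.84, and 5.04 + 1.04 − 2 × 0.51 × 2.16 = 3.88. Average 4.36.
- Half-width = 1.995 × √(2 × 4.36/36) = 0.98. The shift is 0.40/0.98, about 41% of it.
- With equal missingness the gap is zero, so there is no shift when there is no true difference.

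**The case against.** The strongest reply is about context. This is a pilot, section 6.2.1 makes feasibility the primary research question, and the CM pain question is secondary and described as exploratory. That lowers the stakes. It does not turn a nominal/qualitative comparison into a method for mean scores, and a pilot meant to inform a larger trial still needs an estimate with an interval.

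On engagement, a reader might infer that no model at all is linked to total minutes. The documents do not support that. Section 5.2.1 defines engagement activity as total minutes, and 6.4.3.1, headed as primary analyses, lists that label under the count model. What stands is that the methods are unranked and that a count model is a poor match for a duration. Nor can an inflated error rate be claimed: 6.4.1 and 6.4.3 promise corrections for multiple tests, though unnamed.

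A reader might also see an ambiguous measurement window, since 5.2.1 says "Time Frame: through the completion of the study, on average 4 months" while 6.1.4 says that participants "will have 8 weeks of 24-hour access to the program". It changes no number. Section 6.3.6 keeps the app closed until follow-up is complete, so minutes to study end equal minutes over the 8 weeks.

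On covariates, 6.4.1 and 6.4.3 do plan to consider whether they are needed. That is fair, but it leaves the choice until after the data are seen.

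On Cox regression, dropout is listed nearby and could be an event. The text does not connect the two.

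**Conclusion.** The point holds in three parts, all checked by reading. The pain method for app+CM v app does not fit numeric scores and defines no estimate. Cox regression for pre-post differences has no event. The methods for primary outcome 1 are unranked. They should be corrected before analysis, but they do not undermine the trial.

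The figures are illustrations. The drop in power from 56% to 39% applies only if nominal meant a midpoint split at a standardised difference of 0.5.

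A reader might infer that zero-coding produces a bias as large as the confidence margin. The documents do not support this. It would pair a large assumed bias with the narrowest assumed margin, and that margin ignores the extra variance that the zeros add. In one consistent scenario the shift is about 0.4 points against a half-width of about 1.0. Even that rests on an assumed 10-point gap in missingness, and the documents give no missingness by arm. It also removes people from the 36 per arm that 6.4.2 already counts after attrition. Starting from 140/3 = 46.7 per arm, the half-width would be about 0.98 × √(36/46.7) = 0.86, and the shift would be unchanged. Section 6.4.5 also speaks of examining different assumptions. The zero rule is therefore a threat to remove from the pain analysis, not a bias of known size.

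**What to change.** (a) **Pain.** In 6.4.3 and 6.4.3.2, replace the nominal/qualitative method for pain with a between-arm difference (app+CM minus app) in numeric BPI-SF severity and Pain Interference Index scores at T2. Adjust for the baseline score and for gender, the urn randomisation variable in 6.1.2, and report a 95% CI. List both covariates in 6.4.4. In 6.4.5, state that missing pain scores are not coded as zero, and use a likelihood-based model or multiple imputation instead.

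(b) **Cox regression.** In 6.4.3 and 6.4.3.1, delete it for pre-post differences, or restrict it to time to dropout with the time origin and censoring defined.

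(c) **Engagement.** In the same two sections, name one primary analysis of total minutes per participant between the two app arms. One example is the difference in mean minutes with a bootstrap 95% CI, with recorded zeros kept. Label the AR1 mixed model of daily or weekly minutes as supportive.

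The cost is wording in 6.4.3, 6.4.3.1, 6.4.3.2, 6.4.4 and 6.4.5, with no new data. The price is that the freedom to choose among engagement models is given up. The imputation or likelihood model also brings its own assumption, that missingness is explained by the observed data, which should be stated.

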Cognitive Behavior Therapy and Pain Treatment: Cognitive Behavior Therapy (CBT) uses assessment and evaluation of current behaviors to identify problem behaviors and develop skills to manage situations as well as to cope with difficult thoughts and feelings (16,17). CBT typically incorporates normalization of the patient's experience through education, training in strategies for managing disease-related symptoms and other stressors, enhancing self-efficacy, as well as guidance on developing and implementing a long-term self-management plan (18-19). Studies have documented the efficacy of CBT across a wide range of diseases and disorders. A recent meta-analysis showed that the most successful interventions in improving pain and associated functional impairments in adults with chronic pain are rooted in CBT (20). It is well documented that the skills learned through CBT continue, sometimes even increase, after treatment has been completed (21,22). To date, there has been little peer reviewed research within the NF1 population utilizing CBT to treat pain symptoms. CBT like many other psychotherapies has multiple disadvantages: (1) mental health clinicians and practitioners require extensive training in both CBT and pain treatment, (2) limited access to appropriate care of trained clinicians, and (3) formalized face-to-face treatment is relatively expensive. Furthermore, mind-body alternative approaches (MBAA) (i.e., yoga, mindfulness), can have impact on pain intensity and have been found to alter pain experience (23). Research has shown that when CBT and MBAA interventions are combined, they can be effective in decreasing negative emotional

responses to pain, decreasing perceptions of disability, and increasing orientation toward self-management during treatment (24,25). A recent meta-analysis confirmed a combination of CBT and MBAA to be as effective as face-to-face CBT with patients suffering from persistent and chronic pain (26). This same review showed patients preferred mobile-based therapy and had more consistent usage than face to face CBT.

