5. Chronic pain acceptance Chronic Pain Acceptance Questionnaire-Revised (CPAQ-Revised) 20-item scale designed to measure acceptance of pain. The acceptance of chronic pain is thought to reduce unsuccessful attempts to avoid or control pain and thus focus on engaging in valued activities and pursuing meaningful goals will be measured across all groups. The items on the CPAQ are rated on a 7-point scale from 0 (never true) to 6 (always true). To score the CPAQ, add the items for Activity engagement and Pain willingness to obtain a score for each factor. To obtain the total score, add the scores for each factor together. Higher scores indicate higher levels of acceptance [Time Frame: through the completion of the study, on average 4 months.]
6. psychological inflexibility Psychological Inflexibility in Pain Scale (PIPS) 16-item scale used to assess psychological inflexibility (i.e. avoidance, acceptance, fusion, values orientation, dirty discomfort) in people with chronic pain will be measured across all groups. Respondents are asked to rate items on a 7-point scale that ranges from 1 (never true) to 7 (always true). Higher scores indicate greater levels of psychological inflexibility. [Time Frame: through the completion of the study, on average 4 months.]

Other Pre-specified Outcome Measures:

1. Mindfulness based alternative approaches (MBAA) Do individuals with NF1 utilize the MBAA more readily because they are on the mobile application, via Five Facet Mindfulness Questionnaire. 39-item self-completed questionnaire measuring the five facets of mindfulness: Observing (8 items), Describing (8 items), Acting with awareness (8 items), Non-judgmental (8 items), and Non-reactive (7 items). Participants rated the items on a five-point Likert scale (1 = never or very rarely true to 5 = very often or always true), each facet score ranges from 8 to 40, except for the non-reactive facet which ranges from 7 to 35. [Time Frame: through the completion of the study, on average 4 months.]

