6.4.3.3 Analysis of Subject Characteristics

We will evaluate the relationship between iCanCope module use, patterns, gender and change in coping skills and outcomes. Rate and time of specific module use will be evaluated, and LMM will be used to evaluate the relationship between minutes using specific module categories with corresponding change in coping skills efficacy in those categories

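### Secondary question 3 asks about use of mind-body approaches, but its named measure scores mindfulness and its only named test is a moderation interaction

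*Combined protocol and SAP*

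**What the plan says.** Sections 6.4.3 and 6.4.3.2 pose the third of three secondary questions: "Do individuals with NF1 utilize the MBAA more readily because they are on the mobile application". The analysis that follows is moderation: "we will include an interaction term for each separate moderator variable and key predictor of interest". The term is moderator by group for cross-sectional data and moderator by group by time for longitudinal data, tested with a Wald t-test. No moderator, key predictor or outcome is named there, and section 6.4.4 (Subsets and Covariates) is marked N/A.

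Section 5.2.2 lists the same question under Other Pre-specified Outcome Measures and ties it to an instrument: "Do individuals with NF1 utilize the MBAA more readily because they are on the mobile application, via Five Facet Mindfulness Questionnaire". It describes that instrument as a "39-item self-completed questionnaire measuring the five facets of mindfulness", with items rated from 1 to 5 for how true they are.

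MBAA is described in two ways. Section 2.1 has "mind-body alternative approaches (MBAA) (i.e., yoga, mindfulness", which are practices. The outcome label in section 5.2.2 is "Mindfulness based alternative approaches (MBAA", which is narrower.

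Section 6.2.1 gives the third question another meaning: whether participants use MBAA as a means of lessening pain.

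App use is analysed elsewhere. Section 6.4.3.1 compares engagement and the number of activities tried between conditions, and section 6.4.3.3 says "Rate and time of specific module use will be evaluated". Neither is linked to MBAA. Under section 6.1.4 the control group has no access to the app.

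**The concern.** The question is about behaviour and its cause: do people practise MBAA more because they have the app? The measure describes a disposition, and the test concerns effect modification. Followed as written, the plan attaches to this question a p-value that does not bear on it. A non-significant interaction could be read as no increase in use, and a significant one as an increase; neither reading would be justified. A change in mindfulness score could likewise be taken for a change in practice.

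The question matters to the trial's reasoning. The hypothesis in section 4.1 rests on putting CBT and MBAA into the app, and section 3.1 gives as rationale that most patients do not know of MBAA or have not tried it.

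**Working it through.** The plan gives no effect size, standard deviation or power for this question, so there is no stated figure to reproduce. The check sets question, measure and test side by side, and then shows by simulation what the named test responds to.

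**Question against measure.** The question needs a quantity such as sessions, days or minutes of MBAA practice. As section 5.2.2 describes it, the questionnaire yields five facet scores: four with range 8 to 40 (8 items × 1 to 8 items × 5) and one with range 7 to 35 (7 × 1 to 7 × 5). No count or duration of practice is described. Under the section 2.1 meaning, yoga is part of MBAA and nothing in the described scores stands for it. Under the section 5.2.2 label, a mindfulness score is a plausible but indirect proxy, since it can change without practice or stay flat despite it.

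**Question against test.** Write the model for two arms as

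y = b0 + b1·G + b2·M + b3·G·M + error,

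where G is arm and M the moderator. Whether y is higher with the app is a question about b1 (with M centred). The plan names the test of b3. With time added, it names the three-way term rather than group by time.

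**Simulation.** Inputs: 36 per group (section 6.4.2) and alpha 0.05 (section 6.4.1; two-sided is assumed, as sidedness is not stated). Outcome error and moderator are standard normal; 4,000 runs per row; critical t = 1.9955 on 72 − 4 = 68 degrees of freedom. The effect sizes are assumptions.

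| True group effect (SD) | True interaction (SD per SD of M) | Group term rejects | Interaction rejects |
|---|---|---|---|
| 0 | 0 | 4.6% | 4.2% |
| 0.5 | 0 | 53.9% | 4.7% |
| 0.8 | 0 | 91.3% | 4.6% |
| 1.5 | 0 | 100% | 4.8% |
| 0 | 0.5 | 5.6% | 52.5% |

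Rows 1 to 4 show that the interaction test does not respond to a rise in the outcome. Row 5 shows the converse: it can be significant when the average outcome has not risen at all.

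**What a named group contrast could detect** (normal approximation, 80% power, 1.960 + 0.842 = 2.802, before any gain from baseline adjustment):
- both app arms against control, 72 v 36: 2.802 × √(1/36 + 1/72) = 0.57 SD;
- one app arm against control, 36 v 36: 2.802 × √(2/36) = 0.66 SD;
- for comparison, an interaction with a balanced binary moderator, 18 per cell: 2.802 × √(4/18) = 1.32 SD.

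**Where use is logged.** Logs can exist only in the two app arms: 2 × 36 = 72 participants at the final sample size, or about 93 (140 × 2/3) if the 140 expected are randomised equally. The control count is zero. Controls receive education on pain management (section 6.1.1) and are encouraged to use pain websites (section 6.3.1), so MBAA use outside the app is possible and would not be seen in logs.

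**The case against.** A reader might infer that nothing in the plan could bear on the question. The documents do not support that.

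- **The score can be compared by arm.** Section 6.2.1 has the psychometric measures taken at intake, discharge and follow-up, and section 6.3.6 has all three groups complete them. A randomised contrast in mindfulness is therefore estimable, and a conventional interaction model contains the lower-order group and group-by-time terms. This stands, but the plan does not name those terms as the test, and they would show mindfulness rather than use.
- **Another use item may exist.** The instrument table and appendix are not in the text available, so such an item cannot be excluded. This stands as a limit; section 5.2.2 nevertheless assigns the mindfulness questionnaire to this question.
- **Use is already analysed.** Sections 6.4.3.1 and 6.4.3.3 cover activities tried and module use. This stands in part: what is missing is the link to MBAA.
- **Moderation may suit the section 6.2.1 wording.** With MBAA use or mindfulness as moderator and pain as outcome, an interaction could be a sensible exploratory model. This stands, and is a reason not to delete the interaction outright.
- **The tier is low.** The outcome is listed below primary and secondary in a pilot trial, and section 6.4.3.2 presents these analyses as exploratory. This stands and limits the consequence.

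The simulation shows a general property of interaction tests under assumed effects; it estimates nothing about this trial. That misreporting would follow is a risk, not something the documents say.

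**Conclusion.** The point holds in a limited form. The named measure is at best an indirect proxy for use, and the only named test does not address whether use or mindfulness is higher with the app: its rejection rate stayed between 4.2% and 4.8% as the assumed group effect went from 0 to 1.5 SD. Three statements of the question (sections 5.2.2, 6.2.1 and 6.4.3.2) do not agree on what is being asked, and the moderator and outcome are unnamed.

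Two stronger conclusions are not supported: that the trial collects nothing relevant, and that the interaction has no place. A randomised comparison of mindfulness is available, and use can be described in the app arms if the logs identify MBAA content. What cannot be supported, on the documents available, is a claim that use rose because of the app, since controls have no logs and no other measure of use is named. No primary outcome depends on this question.

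**What to change.** 1. Reconcile sections 5.2.2, 6.2.1 and 6.4.3.2 so that one question is asked, with one meaning of MBAA.
2. Name the baseline-adjusted between-arm difference in mindfulness score at T2, app arms against control, as the analysis of that score. Interpret it as mindfulness, not use.
3. Confirm whether MBAA content can be identified in the app logs. Section 6.1.1 lists four app components and labels none as MBAA. If it can, extend the module-use analysis in section 6.4.3.3: report logged MBAA use in each app arm with 95% confidence intervals, and compare CM with no CM.
4. Do not use the interaction test to say whether use is higher. Keep it only as exploratory, with a named moderator and outcome, and only if the section 6.2.1 question is retained.
5. Do not claim that having the app caused greater use.

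The cost is SAP wording plus the log check in step 3. The downside is small: use is described only in the app arms. If the sponsor wants to keep the causal question, a short measure of MBAA use would have to be collected in all three arms, which changes data collection as well as wording.
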